7.3.2 Analyses of Binary Endpoints

The non-responder imputation (NRI) approach will be applied for all binary endpoints, unless otherwise specified. Subjects who discontinued treatment will be classified as non-responders for all the visits following treatment discontinuation.

The odds ratio (OR), relative risk (RR) and absolute risk reduction (ARR) with their confidence interval and associated p-value for BG00011 compared to placebo will be presented.

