7.2.5. Withdrawal From the Study

If a subject is withdrawn from the study, an End of Treatment Visit will be scheduled or performed as soon as possible but within 4 weeks. See [Section 10.2](#) for additional details about withdrawal from the study.

CONFIDENTIAL

The information contained herein may not be used, disclosed, or published without the written consent of
Biogen MA Inc.

7.2.6. **Unscheduled Visit for Acute Exacerbation of IPF**

A subject who experiences a worsening of respiratory status at any time during the study should immediately contact their treating physician. The subject should also notify the Investigator (if different than the treating physician) to determine the need for an IPF Exacerbation Visit.

The IPF Exacerbation Visit should include the following:

- Physical examination
- Vital signs
- Oxygen saturation
- Spirometry
- DL_{CO}
- Imaging studies (chest X-ray or HRCT) if not performed at another facility
- Investigator's determination of IPF exacerbation (see Section 7.2.6.1)

This visit may also include the following:

- ECG
- Clinical laboratory tests at the discretion of the Investigator
- Other tests or evaluations at the discretion of the Investigator

Note: If an IPF exacerbation is suspected at the time of a scheduled visit or is to be evaluated at a scheduled visit, the IPF exacerbation assessments listed above should be included in the scheduled visit if not already included.

A subject who is evaluated, treated, or hospitalized at a facility other than the study site should contact the study site following that visit to determine the need for an IPF Exacerbation Visit. The site assessments at the IPF Exacerbation Visit following an evaluation, treatment, or hospitalization at another facility are the same as those performed at the study site. In addition, study site personnel should obtain sufficient medical records in order to determine the following:

- Possible triggers or causes of the event.
- The results of relevant tests and assessments, including but not limited to:
 - Detailed radiography reports and copies of images of all radiographic examinations (e.g., chest X-ray or HRCT scan) for submission to the central imaging vendor.
 - Spirometry, lung volume, and/or DL_{CO} testing reports.
- Descriptions of the severity and duration of the event.
- Details of the medical treatment provided, including relevant medications and other major elements of the clinical management.

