10. DISCONTINUATION OF STUDY TREATMENT AND WITHDRAWAL OF SUBJECTS FROM THE STUDY

10.1. Discontinuation of Study Treatment

Study treatment discontinuation is defined as the premature ending of study treatment dosing, i.e., when a subject permanently stops taking the study treatment before the last dose (the Week 51 dose). Reasons for mandatory study treatment discontinuation are listed in Section 10.1.1. The primary reason for study treatment discontinuation must be recorded in the subject's CRF.

Subjects who discontinue study treatment must return for an End of Treatment Visit as soon as possible, but within 4 weeks after discontinuation of treatment. All assessments planned for the Week 52 Visit except the HRCT scan will be performed. If the End of Treatment Visit occurs in the visit window for the next scheduled visit, then the scheduled visit may serve as the End of Treatment Visit, and all assessments for the End of Treatment Visit should occur at that time. Subjects will go on to complete all remaining visits as scheduled, including the Week 52 and Safety Follow-Up Visits (see Table 2 for a list of assessments to occur at the End of Treatment and Safety Follow-Up Visits).

Note: A subject who misses 1 or more doses of study treatment should restart study treatment, receive all remaining doses, and complete all remaining study visits.

See Section 10.2 for information related to the withdrawal of subjects from study.

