10.2. Withdrawal of Subjects From the Study

Study withdrawal is defined as the premature ending of study visits and assessments. The reasons for mandatory study withdrawal are listed below (Section 10.2.1). Note that discontinuation of study treatment does not require withdrawal from the study if a subject continues to attend clinic visits and complete assessments.

If a subject is withdrawn from the study, an End of Treatment Visit will be scheduled or performed as soon as possible but within 4 weeks. All assessments planned for the Week 52 Visit except the HRCT scan will be performed (see Table 2 for a list of assessments to occur at the End of Treatment Visit).

If a subject is unwilling or unable to attend, at minimum, the End of Treatment Visit, and decides to withdraw consent, the reason for withdrawal will be documented and no further assessments will be obtained.

Subjects who are withdrawn from the study will not be replaced.

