6.1.1.4 Early Termination or Unscheduled Visits for Acute Exacerbation of IPF

In general, when data are summarized by analysis visit, the Early Termination Visit or Unscheduled Visits for Acute Exacerbation of IPF will be assigned to an appropriate scheduled analysis visit by using a window scheme provided in Table 1.

Table 1: Visit Windows for Early Termination or Unscheduled Visits

Scheduled Visit Time	Target study day	Analysis visit window (days)	
		Efficacy & Safety Data	PK Data
Baseline (Day 0)	1	Most recent non-missing value on/before the date of first dose	
Day 5*	6	N/A	[6,7]
Week 4	29	[2,43]	[8,43]
Week 8	57	[44,71]	
Week 12	85	[72,99]	
Week 16	113	[100,127]	
Week 20	141	[128,162]	
Week 26	183	[163,203]	
Week 32	225	[204,246]	
Week 38	267	[247,288]	
Week 44	309	[289,337]	
Week 52	365	[338,393]	
Safety Follow-up (Week 60)	421	
 • If subject who discontinued treatment due to reasons other than study termination by sponsor: > min (393, study day of each subject's week 52/EOT visit in treatment period) ** • If subject who discontinued treatment due to study early termination by sponsor: > min (393, study day of each subject's last dose) 	

*The Day 5 Visit is for blood collection only (for PK analysis) and may be done in the clinic or at home (by appropriate personnel). Sample collection should occur on Day 5 (not sooner), with a +1 day window allowed (i.e., collection should occur on Day 5 but may occur on Day 6).

** For subjects who discontinued the treatment due to reasons other than study termination by sponsor will go on to complete all scheduled visits until either week 52 or the study was terminated by sponsor due to the urgent safety measure whichever occurs first. The Week 52/ EOT visit in treatment period is defined as the last visit scheduled for either week 52 or study termination due to the urgent safety measure.

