7.3.2.1 IPF Acute Exacerbation

The secondary efficacy endpoint, proportion of subjects with at least 1 acute exacerbation (using modified diagnostic criteria for acute IPF exacerbation derived from [Collar 2007]) during the 52 weeks on study, will be analyzed using the binary endpoint analyses described in [Section 7.3.2](#).

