7.3.2.2 Pulmonary Function Tests

The secondary efficacy endpoint, number of subjects with absolute decline of 10% predicted in FVC (i.e. $\text{FVC percent predicted}_{\text{baseline}} - \text{FVC percent predicted}_{\text{progression}} \geq 10\%$) over 52 weeks will be analyzed using the binary endpoint analyses described in [Section 7.3.2](#). Subject with absolute decline of 10% predicted in FVC at any scheduled visits will be considered as subject with absolute decline of 10% predicted in FVC regardless whether the percent predicted FVC decline is less than 10% afterward and before the study early termination.

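### SAP 7.3.2 applies non-responder imputation to two adverse ever/never endpoints without saying whether a discontinuer counts as an event, and neither coding gives the endpoint as defined

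*SAP*

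**What the plan says.** SAP 7.3.2 makes non-responder imputation the default for every binary endpoint and gives the rule visit by visit: "Subjects who discontinued treatment will be classified as non-responders for all the visits following treatment discontinuation". It then asks for the odds ratio, relative risk and absolute risk reduction with confidence intervals and p-values.

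Two readable endpoints use this section. SAP 7.3.2.1 sends the proportion with an acute exacerbation "during the 52 weeks on study, will be analyzed using the binary endpoint analyses described in" Section 7.3.2 and states no exception. SAP 7.3.2.2 does the same for the 10-point FVC decline, and adds that a "Subject with absolute decline of 10% predicted in FVC at any scheduled visits" counts even if it later reverses.

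Protocol Version 1, on which the SAP is based, keeps discontinuers under observation. Section 10.1 says "Subjects will go on to complete all remaining visits as scheduled", and Section 10.2 says that "discontinuation of study treatment does not require withdrawal from the study if a subject continues to attend clinic visits". The footnote to SAP Table 1 agrees: subjects who stop for reasons other than sponsor termination "will go on to complete all scheduled visits until either week 52 or the study was terminated by sponsor". Protocol 7.2.6 covers exacerbations throughout: "A subject who experiences a worsening of respiratory status at any time during the study should immediately contact their treating physician".

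**The concern.** Non-responder imputation suits a favourable outcome, where a subject who stops treatment is denied credit for success. Both endpoints here are failures, so the term has two opposite meanings and the readable text does not choose between them. The rule also acts on visits, while each endpoint is one value per subject.

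If non-responder means event, the odds ratio, relative risk and risk difference partly measure who stopped treatment. If it means no event, exacerbations that the protocol takes care to observe may drop out of the proportion. The trial stopped on a safety imbalance (SAP Section 1), so the proportions with adverse respiratory events should not depend on an unstated programming choice.

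**Working it through.** **Inputs.** The documents give no event or discontinuation counts for this trial and no planned figure for these two endpoints, so there is nothing of the plan's to reproduce. All rates below are assumptions unless a source is named. Risks and ratios are BG00011 versus placebo.

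**1. Coded as event (both endpoints).** Let p be the true risk and d the share of event-free subjects recoded because they stopped treatment. This d is not the 15% study dropout in SAP Section 4. The reported risk is p* = p + (1 − p)d. For example, 0.20 + 0.80 × 0.10 = 0.28 and 0.10 + 0.90 × 0.10 = 0.19, so RR = 0.28/0.19 = 1.47.

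| True risks | d | Reported risks | RR | OR | Difference, points |
|---|---|---|---|---|---|
| 20% vs 10% | none | 20.0% vs 10.0% | 2.00 | 2.25 | 10.0 |
| 20% vs 10% | 5% both | 24.0% vs 14.5% | 1.66 | 1.86 | 9.5 |
| 20% vs 10% | 10% both | 28.0% vs 19.0% | 1.47 | 1.66 | 9.0 |
| 20% vs 10% | 20% both | 36.0% vs 28.0% | 1.29 | 1.45 | 8.0 |

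Equal stopping therefore pulls RR towards 1. With no true effect (15% in both arms), unequal stopping creates a difference:

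- d = 15% vs 10%: 27.75% vs 23.5%, RR 1.18
- d = 20% vs 10%: 32.0% vs 23.5%, RR 1.36
- d = 10% vs 20%: 23.5% vs 32.0%, RR 0.73

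Protocol 4.3 gives 17% versus 32% for a meaningful FVC decline on pirfenidone and placebo. Borrowing those as the two arms' risks (RR 0.53, OR 0.44), d = 15% in both arms gives 29.45% vs 42.2% (RR 0.70, OR 0.57). With d = 25% vs 15%, the result is 37.75% vs 42.2% (RR 0.89, OR 0.83).

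**2. Coded as no event (exacerbation).** Let s be the share of subjects with an exacerbation whose first one follows discontinuation. Then p* = p(1 − s). From 20% vs 10%:

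- s = 10% in both arms: 18.0% vs 9.0%, RR still 2.00
- s = 25% vs 10%: 15.0% vs 9.0%, RR 1.67
- s = 10% vs 25%: 18.0% vs 7.5%, RR 2.40

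FVC decline is largely spared under this coding, because SAP 7.3.2.2 counts a decline at any scheduled visit and 7.3.2 gives way where something else is specified.

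**3. Both codings on the same data.** Assume a 10% risk in both arms, discontinuation of 25% vs 15%, the same risk in discontinuers, and half of discontinuers' first events falling after they stop. The true OR is 1.00.

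- Event: 0.75 × 0.10 + 0.25 = 32.5%, against 0.85 × 0.10 + 0.15 = 23.5%; OR 1.57
- No event: 0.75 × 0.10 + 0.5 × 0.25 × 0.10 = 8.75%, against 0.85 × 0.10 + 0.5 × 0.15 × 0.10 = 9.25%; OR 0.94

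Over risks from 5% to 16%, the event-coded OR runs from 1.69 to 1.47 and the no-event OR stays at 0.94. The upper risk is the Phase 2a figure in Protocol 4.4.3: 5 of 31 treated subjects with an exacerbation reported as an AE. On these inputs the unstated choice changes the direction of the estimate.

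**4. Why follow-up time belongs in the fix.** With a constant hazard and a 15% risk over 52 weeks in both arms, the observed risk at w weeks is 1 − 0.85^(w/52). That is 7.8% at 26 weeks and 10.1% at 34 weeks, so RR is 0.77 with no true effect.

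**The case against.** The case on the other side has several parts.

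- **Limited consequence.** SAP 6.7 makes all inference nominal. Exacerbations also appear in a Kaplan-Meier curve (7.3.3.2) and an AE listing (8.2.1), and FVC decline enters the progression composite (7.3.3.1). This stands as a limit on impact, but none of these outputs corrects the estimates that 7.3.2 orders.
- **Unseen material.** The TFL shells are not supplied and Section 7.4 is redacted, so a definition there cannot be ruled out. Section 7.3.2 points to neither.
- **One sentence of definition would do.** It would remove the ambiguity, but either code would still depart from an exacerbation endpoint defined over the 52 weeks on study. Treating discontinuation as failure is legitimate, but it is a different, composite endpoint.
- **Consistency with the SAP.** A reader might infer that the imputation contradicts the SAP's own practice, because the complementary analysis (7.2.3) keeps data after discontinuation. The documents do not support that: the primary FVC analysis (7.2.1) censors at discontinuation. Practice is mixed and gives no argument either way.
- **Sponsor termination.** A reader might also infer that every event-free subject on treatment at termination becomes an event, because SAP Tables 1 and 4 contain the phrase "If subject who discontinued treatment due to study early termination by sponsor". Those tables only set visit windows. Table 1 places such subjects' early-termination or unscheduled records after the last dose in Safety Follow-up, where the protocol schedules no spirometry, so generally no treatment-period visit is left to classify. Whether termination triggers the rule is an open point, and large recoding shares should not be used as headline figures.

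**Conclusion.** The point holds and should be fixed. An operative imputation rule is applied to two adverse endpoints that it does not fit. The event code affects both endpoints; the no-event code essentially affects exacerbation only.

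The size depends on stopping rates that the documents do not give. At assumed recoding shares of 5% to 20% in both arms, a true RR of 2.00 is reported as 1.66 to 1.29. Assumed shares of 20% vs 10% produce an RR of 1.36 from no effect. Under the no-event code the RR is distorted only if the share of exacerbations falling after discontinuation differs between arms, although the risk difference shrinks even when the shares are equal. These figures show what the rule can do; they do not estimate what happened in this trial.

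**What to change.** Remove non-responder imputation for these two endpoints. Count every observed exacerbation, and every decline of 10 points or more observed at a scheduled visit as 7.3.2.2 defines it, up to Week 52 or study termination, whichever is first, regardless of treatment discontinuation. State that sponsor termination is the administrative end of follow-up.

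The downside is that an observed proportion treats event-free early withdrawals as having no event. So report follow-up time by arm beside the proportions, or report Kaplan-Meier risk at a named week. The second option should say how death, lung transplantation, withdrawal and the background-therapy censoring in 7.3.3 are handled. If discontinuation is meant to count as failure, present it as a separate, named composite that excludes sponsor termination, beside the observed-event result.

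The cost is SAP wording and simpler programming; no new data are needed, and SAP 1.1 allows documented revisions.

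As a separate minor point, SAP Section 1 limits all endpoints except the primary, percent predicted FVC and two DLco measures to descriptive statistics. The Week 26 TLC mixed model (7.3.1.1), the p-values in 7.3.2, and the Cox model and log-rank test for progression (7.3.3, 7.3.3.1) go beyond that. Either extend the exception list or drop the extra tests.

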7.3.2.1 IPF Acute Exacerbation

The secondary efficacy endpoint, proportion of subjects with at least 1 acute exacerbation (using modified diagnostic criteria for acute IPF exacerbation derived from [Collar 2007]) during the 52 weeks on study, will be analyzed using the binary endpoint analyses described in [Section 7.3.2](#).

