2 STUDY OBJECTIVES AND ENDPOINTS

Primary Objective	Primary Endpoints
To evaluate the efficacy of BG00011 compared with placebo in subjects with IPF.	Yearly rate of change in forced vital capacity (FVC, expressed in mL over 52 weeks) in subjects randomized to BG00011 compared with placebo.
Secondary Objectives	Secondary Endpoints
To evaluate the efficacy of BG00011 compared with placebo in subjects with IPF as determined by change in percent predicted FVC.	Yearly rate of change in FVC, expressed in percent predicted, over 52 weeks.
To assess progression-free survival in subjects who receive BG00011 compared with placebo.	
Time to progression, as defined by a composite endpoint, including any of the following events:
 
 • Absolute decline of 10% predicted in FVC (FVC percent predicted_{baseline} – FVC percent predicted_{progression} ≥10%). • Nonelective hospitalization for respiratory events. • Lung transplantation or death.
To assess the occurrence of IPF exacerbation (using modified diagnostic criteria for acute IPF exacerbation derived from [Collard 2007]) in subjects who receive BG00011 compared with placebo.	
 • Time to first acute exacerbation, measured in days. • Proportion of subjects with at least 1 acute exacerbation during the 52 weeks on study. • Number of exacerbations during 52 weeks.
To assess the incidence of absolute decline in FVC ≥10% in subjects who receive BG00011 compared with placebo.	Number of subjects with absolute decline of 10% predicted in FVC (FVC percent predicted _{baseline} – FVC percent predicted _{progression} ≥10%) over 52 weeks.
To assess the time to death or lung transplantation in subjects who receive BG00011 compared with placebo, and the transplant-free survival rate at Week 26 and Week 52.	Time to death or lung transplantation, measured in days.

To assess the time to nonelective hospitalizations in subjects who receive BG00011 compared with placebo,
	
Time to all nonelective hospitalizations and to nonelective respiratory hospitalizations, measured in days.

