4 SAMPLE SIZE JUSTIFICATION

The sample size calculation is based on the annual declining rate in FVC (mL/year). With 145 subjects randomized per arm, and assuming a 15% dropout rate over a 1-year treatment period, the study has approximately 80% power to show that the BG00011 treatment arms differentiate from the arm without BG00011 at a 2-sided 15% α level, given a treatment effect of 82.5 mL/year with a common standard deviation of 280 mL. The calculation is based on the assumption that the FVC decline rate in subjects receiving placebo and no background therapy is 220 mL/year, and in subjects receiving background but no BG00011 therapy it is assumed to be 110 mL/year. A 60% reduction in the FVC decline rate in the subjects receiving placebo would be a treatment effect of 132 mL/year. A 30% reduction in the FVC decline rate in subjects receiving background therapy would be a treatment effect of 33 mL/year. With the assumption that 50% of each type of subject are randomized in the study, the combined treatment effect is approximately 82.5 mL/year. The 15% dropout rate for this study was estimated based on prior experience for the placebo arms in the Phase 3 studies for nintedanib and pirfenidone [King 2014; Richeldi 2014].

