7.3 Analysis of Secondary Efficacy Endpoints

7.3.1 Analysis of Continuous Endpoints

7.3.1.1 Pulmonary Function Tests

The continuous secondary efficacy endpoint of change from baseline in percent predicted FVC, at week 26 and week 38 will be applied using the primary analysis, supplementary analysis and complementary analysis described in [Section 7.2](#).

The continuous secondary efficacy endpoints listed as follows will be applied using MMRM model described in [Section 7.2.2](#). Similarly, if less than 20 subjects (i.e. <20 subjects) had non-missing measurements for any endpoint at a given visit time of interest, the mean difference comparison will not be performed at that visit time for that endpoint due to the insufficient data.

- Change from baseline in DL_{co}, corrected for hemoglobin (DL_{co}/Hb) at weeks 26 and 38, respectively.
- Change from baseline in percent (%) predicted DL_{co}/Hb at weeks 26 and 38, respectively.
- Change from baseline in TLC at weeks 26
- Change from baseline in percent (%) predicted TLC at weeks 26

Because the study stopped early, the following continuous secondary efficacy endpoints could not be evaluated with insufficient data.

- Changes from baseline in percent (%) predicted FVC over 52 weeks
- Changes from baseline in DL_{co}/Hb absolute over 52 weeks.
- Changes from baseline in percent (%) predict DL_{co}/Hb over 52 weeks.
- Changes from baseline in total lung capacity (TLC), as measured by plethysmography, over 52 weeks.

- Changes from baseline in percent (%) predicted TLC over 52 weeks.

All the continuous secondary endpoints listed below will be summarized by descriptive statistics at each scheduled visit time. The measurement and change from baseline will be presented. Plots of mean value with standard error for each of the following continuous secondary endpoints at each visit will also be presented.

- FVC
- Percent (%) predicted FVC
- DL_{co}/Hb
- Percent (%) predicted DL_{co}/Hb
- Total lung capacity (TLC), as measured by plethysmography
- Percent (%) predicted TLC

7.3.1.2 6-Minute Walk Test (6MWT)

6MWT distance and change from baseline in 6MWT distance will be summarized and presented by descriptive statistics at each scheduled visit time.

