7.3.3.2 Other Time-to-Event endpoints

The time-to-event types secondary efficacy endpoints listed as follows will be applied only by the Kaplan-Meier curve method where number of subjects at risk at each visit and the proportion of subjects who progressed in each treatment group will be summarized and presented.

- Time to first acute exacerbation (using modified diagnostic criteria for acute IPF exacerbation derived from [Collar 2007]), measured in days.
- Time to death or lung transplantation measured in days.
- Time to all nonelective hospitalizations, measured in days.
- Time to all nonelective respiratory hospitalizations, measured in days.

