7.3.4 Analysis of Other Endpoints

7.3.4.1 Number of Occurrences

The secondary efficacy endpoint, number of exacerbations during 52 weeks, defined by using the 2007 modified diagnostic criteria [Collard 2007], a listing will be provided if less than 4 subjects in each treatment group in which each subject experiences more than one exacerbation during the study period. If no fewer than 4 subjects in either treatment group in which each subject experience more than one exacerbation during the study period, a table of summary descriptive statistics will be provided with its associated listing.

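### After early termination, the exacerbation and FVC-decline endpoints keep a 52-week label but ignore time at risk, so their absolute risks, ARRs and counts are not 52-week figures

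*SAP*

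**What the plan says.** SAP Section 1 records that the trial was stopped on the DSMB's recommendation of 16 August 2019. The SAP adapts in several places. Section 7.2.1 moves the primary comparison to Weeks 26 and 38. Section 7.3.1.1 says of the 52-week lung-function changes: "Because the study stopped early, the following continuous secondary efficacy endpoints could not be evaluated with insufficient data". Section 7.3.3 censors event-free subjects at their last assessment in the treatment period.

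Three endpoints are not adapted:

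- Exacerbation (7.3.2.1): the proportion with at least one event "during the 52 weeks on study, will be analyzed using the binary endpoint analyses".
- FVC decline (7.3.2.2): the number with a fall of 10% predicted "over 52 weeks will be analyzed using the binary endpoint analyses".
- Number of exacerbations in 52 weeks (7.3.4.1): "a listing will be provided if less than 4 subjects in each treatment group" had repeat events, otherwise a descriptive table. Neither output uses person-time.

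Section 7.3.2 gives the first two an OR, RR and ARR with confidence interval and p-value. It applies non-responder imputation (NRI) to everyone who discontinued treatment. It does not say whether a non-responder is a subject with or without the event, and it does not exempt subjects stopped by the sponsor.

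Section 2 lists the "transplant-free survival rate at Week 26 and Week 52" among the objectives. For death or transplant, 7.3.3.2 specifies a Kaplan-Meier curve, numbers at risk, and that "the proportion of subjects who progressed in each treatment group will be summarized and presented". It specifies no estimate at either week.

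**The concern.** A proportion taken over subjects followed for different lengths of time depends on how accrual fell relative to the stopping date. It does not estimate the risk at 52 weeks, or at any other fixed time. Readers will nevertheless take a result labelled as 52 weeks, with an ARR and p-value, at face value and set it beside 52-week results from other IPF trials. The same holds for a count of exacerbations with no denominator in time. Absolute risks and risk differences express how much benefit or harm there was, which matters in a trial stopped for a safety imbalance. The SAP recognises the problem for continuous endpoints, so leaving it here is an internal inconsistency.

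**Working it through.** **The plan's own figure.** The only design calculation in the SAP is the power statement in Section 4: "With 145 subjects randomized per arm, and assuming a 15% dropout rate over a 1-year treatment period", tested "at a 2-sided 15% α level, given a treatment effect of 82.5 mL/year with a common standard deviation of 280 mL". Evaluable per arm: 145 × 0.85 = 123.25. Standard error: 280 × √(2/123.25) = 35.7 mL. Effect over standard error: 82.5/35.7 = 2.31. The two-sided 15% critical value is 1.44, so power = Φ(2.31 − 1.44) ≈ 0.81, matching the stated 80% or so. The SAP gives no risk, ARR or follow-up figure for the binary or count endpoints, so what follows rests on stated assumptions.

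**Inputs.** Planned follow-up is 52 weeks (SAP 3). The documents give no follow-up distribution at termination. Protocol version 1 is dated 20 November 2017 and the DSMB met on 16 August 2019: 634 days, or 90.6 weeks. Allowing 5 weeks for screening, entry could span at most about 85 weeks. Assumed 52-week risks are (a) 10% and 20%; (b) 32% and 17%, borrowed from the pirfenidone results for FVC decline in Protocol 4.3, one of which comes from a 72-week study; (c) 10% and 5%. Hazards are assumed constant.

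**Reading 1: a non-responder has no event.** With h = −ln(1 − p) per year, the observed proportion is the average of 1 − exp(−hT) over follow-up T in years.

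For T uniform over 0 to 1 year this is 1 − p/h:

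- p = 0.10: h = 0.1054, giving 5.1%.
- p = 0.20: h = 0.2231, giving 10.4%.
- Difference: 5.3 points against a true 10, ratio 0.53.

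Other patterns for the same risks: uniform over 13 to 52 weeks gives 6.35% and 12.92%, ratio 0.66. Half the subjects with full follow-up and half uniform over 0 to 52 weeks gives 7.54% and 15.19%, ratio 0.76.

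For inputs (b) and (c), with everyone followed for T weeks, the observed risk is 1 − (1 − p)^(T/52):

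| Follow-up (weeks) | ARR ratio, 32% v 17% | ARR ratio, 10% v 5% |
|---|---|---|
| 13 | 0.31 | 0.27 |
| 20 | 0.46 | 0.40 |
| 26 | 0.58 | 0.52 |
| 32 | 0.69 | 0.63 |
| 38 | 0.79 | 0.75 |
| 44 | 0.88 | 0.86 |

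At 26 weeks the 32% v 17% case gives 17.5% v 8.9%, an ARR of 8.6 points against 15.0. Uniform entry over the full 85 weeks (mean follow-up 36 weeks) gives ratios of 0.73 and 0.70.

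The RR hardly moves. For 32% v 17% it runs from 0.495 to 0.524 across the table, against 0.531 at 52 weeks. For a harmful effect, 10% v 5%, it runs from 2.04 to 2.01 against 2.00.

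**Reading 2: a non-responder has the event.** If a share s of event-free subjects is discontinued, the reported risk is c + (1 − c)s and the ARR is multiplied by (1 − s). With the 26-week proportions above as c:

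| s (assumed) | Risks | ARR (points) |
|---|---|---|
| 0.15 | 29.9% v 22.6% | 7.3 |
| 0.50 | 58.8% v 54.4% | 4.3 |
| 0.80 | 83.5% v 81.8% | 1.7 |

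Table 1 in SAP 6.1.1.4 has a category for subjects who discontinued treatment because the sponsor ended the study. On the text of 7.3.2, those subjects fall under NRI.

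**Counts.** With a constant event rate, the mean count per subject is the rate times mean follow-up. Relative to 52 weeks the ratio is 13/52 = 0.25, 26/52 = 0.50 or 44/52 = 0.85.

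**The case against.** The SAP does use follow-up time elsewhere. Section 7.3.3.2 gives Kaplan-Meier curves for time to first exacerbation and for death or transplant, from which Week 26 values could be read by eye. The 10% FVC decline enters the progression composite in 7.3.3.1, which has Cox and stratified log-rank analyses. Section 8.2 lists incidence rates of adverse events, and 6.7 makes all inference nominal. This stands, and it lowers the stakes. It does not close the gap: no fixed-week estimate or between-arm difference is specified for first exacerbation, FVC decline has time-to-event handling only inside the composite, and the 52-week OR, RR and ARR would still be printed.

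A second objection is that Section 1 restricts endpoints other than the primary and key secondary ones to descriptive statistics, so more modelling is out of place. That is fair against a mandatory rate-ratio model. It does not tell against fixed-week estimates with intervals, and 7.3.2 already departs from Section 1 by giving p-values.

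Three stronger readings may tempt a reader:

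- *The reported risks are certainly too small, by about half.* That direction holds only on the no-event reading of NRI. Even then, about half needs mean follow-up near 20 to 26 weeks, which the documents do not show.
- *The problem is separate from how discontinuers are coded.* It is not, because the SAP classes subjects cut off by the sponsor as treatment discontinuers.
- *The relative risk is biased.* This would need follow-up to differ by arm. Allocation is 1:1 and stratified, termination applied to both arms, and nothing in the documents shows an imbalance.

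**Conclusion.** The point holds, as a should-fix. The binary and count outputs in 7.3.2.1, 7.3.2.2 and 7.3.4.1 will not be 52-week figures, and the Week 26 and Week 52 transplant-free survival rates have no specified estimate.

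On the no-event reading of NRI, the ARR is about 0.3 to 0.9 of its 52-week value under constant hazards and follow-up balanced by arm. On the event reading, the ARR shrinks towards zero, and risks go well above their 52-week values once a large share of subjects is discontinued. Which applies cannot be settled from the SAP, and neither can the size, because the follow-up distribution is not given. RR is little affected on the no-event reading. These are secondary efficacy summaries, and the stopping-rule events named in Protocol 7.3 are different ones (deaths, transplants, FVC declines of 15% predicted or more), so nothing stronger than should-fix is warranted.

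**What to change.** - **7.3.2.1 and 7.3.2.2:** report the risk at Week 26, and at Week 38 if enough subjects remain at risk, by arm. Estimate it by cumulative incidence with death and transplant as competing events, and give the between-arm difference with a 95% CI.
- **NRI:** do not apply it to subjects stopped by sponsor termination; censor them at last assessment, as 7.3.3 does. Wherever NRI is kept, state whether a non-responder counts as an event.
- **Labels:** describe any retained proportion as *by study termination*.
- **7.3.3.2:** print Kaplan-Meier transplant-free survival at Week 26, and at Week 52 if estimable, with CI.
- **7.3.4.1:** always tabulate events, person-years and the rate per 100 person-years by arm. A modelled rate ratio is optional.

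The cost is SAP wording and a few table rows. The analyses in 7.3.3 already need event and censoring dates, and 8.2 already calls for incidence rates. Estimates at later weeks will be less precise. Since SAP 1.1 has the plan finalised before Part I lock and unblinding after it, the change belongs before that lock.
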